7.1 Screening

7.1.1 Within 28 days prior to registration for protocol therapy:

- Informed consent prior to research specific testing
- Radiological assessment (CT or MRI of chest, abdomen, and pelvis) with tumor measurements
- Identification of available paraffin embedded block or adequate unstained slides of archived tumor tissue (primary or metastatic based on availability).
 - **NOTE:** if adequate archived tissue is unavailable, excisional or percutaneous core tumor biopsy is required for research purposes.
- OPTIONAL SUB-STUDY ANALYSIS: For subjects who have archival tissue from primary site, and who agree to the exploratory sub-study analysis comparing PD-L1 expression in primary tumor tissue versus metastatic post first-line chemotherapy tumor tissue, perform excisional or percutaneous core tumor biopsy for research.

7.1.2 Within 14 days prior to registration for protocol therapy unless otherwise noted:

- Eligibility evaluation (review of inclusion and exclusion criteria)
- Medical history
- Physical examination
- Vital signs including Blood pressure, Weight [kg] Height [cm] (SCREEN ONLY) and ECOG PS
- Laboratory testing:
 - Complete metabolic profile (CMP) will include: serum chemistries (creatinine, glucose, total protein, blood urea nitrogen [BUN], total carbon dioxide [CO₂], albumin, total bilirubin, alkaline phosphatase, and aspartate transaminase [AST] and alanine transaminase [ALT]) and electrolytes (total calcium, chloride, potassium, sodium).
 - CBC (including platelets, ANC & HGB)
 - PT/INR and aPTT
 - TSH, T3 and T4 tests are done. For T3 and T4, free versus total is at the site investigator's discretion
 - Serum pregnancy test for female subjects of childbearing potential (within three days of registration for protocol therapy).
- Smoking History Questionnaire (Appendix A)
- Charlson Comorbidity Index assessment (See SPM for form)
- Record Adverse Events and concomitant medications

7.2 On Treatment: Day 1 of each Cycle (\pm 3 days) unless otherwise noted:

On Day 1 of each treatment cycle, the following assessments/treatment administrations will occur: (NOTE: For Cycle 1 Day 1 ONLY, required tests do not need to be repeated if done within 7 days prior)

- Physical examination
- Vital signs including Blood pressure and Weight [kg] and ECOG PS
- Laboratory testing:
 - CMP will include: serum chemistries (creatinine, glucose, total protein, BUN, total CO₂, albumin, total bilirubin, alkaline phosphatase, and AST and ALT) and electrolytes (total calcium, chloride, potassium, sodium)
 - CBC (including platelets, ANC & HGB)
 - TSH, T3 and T4 tests are done on Day 1 of even numbered cycles only (i.e., Cycle 2, 4, 6, etc.). For T3 and T4, free versus total is at the site investigator's discretion
 - Correlative studies: Blood sample collection (See Table 7 above for correlative sample schedule)
- Record Adverse Events and any changes to concomitant medications
- Restaging CT or MRI of the chest, abdomen, and pelvis is performed after every four cycles of treatment (i.e., approximately every 12 weeks). Make every effort to perform the same imaging modality throughout the study.
- Pembrolizumab or placebo administration (IV)

7.3 Progression/Unblinding/End of Treatment (EOT)

Treatment will be discontinued if there is evidence of disease progression or unacceptable toxicity or if the subject stops participating or withdraws from the study. After the first documentation of progression per RECIST 1.1, if the subject is clinically stable, confirmatory scans should be performed 4-6 weeks later (see Section 7.3.2 for details).

7.3.1 End of Treatment Visit: 30 days after last dose of study drug (\pm 7 days)

- Physical examination
- Blood pressure
- Weight [kg]
- ECOG PS
- Laboratory testing:
 - CMP will include: serum chemistries (creatinine, glucose, total protein, BUN, total CO₂, albumin, total bilirubin, alkaline phosphatase, and AST and ALT) and electrolytes (total calcium, chloride, potassium, sodium)
 - CBC (including platelets, ANC & HGB)
 - Correlative studies: Blood sample collection (see Table 7 above for correlative sample schedule)
- Record Adverse Events and changes to concomitant medications
- Subjects will continue to be followed until resolution or stabilization of any treatment-related toxicities.
- Radiological assessments (only if >28 days since last assessment).

7.3.2 Unblinding

Blinding of the treatment assignment is critical to the integrity of this clinical study. There are situations, however, in which unblinding is necessary. The patient's safety takes priority over any other considerations in determining if the treatment assignment should be unblinded. Before breaking the blind of an individual patient's treatment, the site investigator should determine that the unblinded information is necessary. **The decision to unblind the treatment assignment will be discussed with the sponsor-investigator, but the site investigator always has ultimate authority for the decision to unblind.**

Situations in which unblinding is necessary include but are not limited to:

- Time of treatment discontinuation due to disease progression
- Time of treatment discontinuation due to unacceptable toxicity
- A medical event in an individual subject in which knowledge of the investigational product is critical to the subject's clinical management.

Because of the various situations that can lead to unblinding, and the potential impact of unblinding on the primary endpoint, the following approach will be utilized:

- Patients who are unblinded for toxicity and confirmed to be on pembrolizumab, but who meet criteria for continued treatment with pembrolizumab due to effective management of the toxicity as per 5.1, may continue pembrolizumab and will be followed for the primary endpoint of progression as per section 7.6.
- Patients who are unblinded for a first progression event and confirmed to be on pembrolizumab, but who are considered clinically stable and suitable by the treating investigator for ongoing treatment while awaiting confirmatory scans 4-6 weeks later as per 7.6 may continue pembrolizumab until progression is confirmed. If progression is confirmed at the follow-up scan as outlined in 7.6, the initial date of progression will be considered the progression date. If progression is not confirmed, patients may continue treatment with pembrolizumab.

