7 STUDY SCHEDULE OF EVENTS

	Screening		On Treatment Cycle = 3 weeks (up to 24 months)	Progression/Unblinding EOT ¹⁵	Cross-over to pembrolizumab	Follow-up
	-28 days	-14 days				
REQUIRED ASSESSMENTS						
Eligibility evaluation (review of inclusion and exclusion criteria) ¹	X	X				
Medical history		X				
Physical examination		X				
Vitals and ECOG performance status ²		X				
Charlson Comorbidity Index		X				
Smoking History Questionnaire ³		X				
AEs & concomitant medications		X				
LABORATORY ASSESSMENTS						
CMP ⁴		X				
CBC ⁴		X				
PT/INR and aPTT ⁵		X				
Thyroid Function (TSH, T3 and T4) ⁶		X				
Serum pregnancy test ⁷		X ⁷				
DISEASE ASSESSMENT						
CT or MRI of chest, abdomen, and pelvis	X ¹²					
TREATMENT EXPOSURE						
pembrolizumab or placebo (IV)						
CORRELATIVE STUDIES						
Archival tumor tissue for research ⁸	X					
Tumor Biopsy if archival tissue not available ⁸	X					
Tumor Biopsy for sub-study analysis ⁸	X					
Blood samples for research ⁹						
FOLLOW-UP						
For progression, start date of additional cancer treatment, and survival ¹⁴						X ¹⁴

RANDOMIZATION

1. Subjects should undergo informed consent prior to any research specific testing being performed. Subjects randomized to Arm A (placebo) who discontinue treatment due to progression or unacceptable toxicity will be eligible to cross over to pembrolizumab provided eligibility outlined in section 3 is met. (**NOTE:** inclusion criteria #6 regarding initiation of study treatment within 2 to 6 weeks of completing first line chemotherapy only applies to initial randomization to placebo). Cross over treatment should be initiated within 4 weeks of confirming eligibility. Subjects initiating treatment with pembrolizumab from placebo will follow the same schedule outlined in the calendar above and receive up to 24 months of treatment unless progression or unacceptable toxicity is experienced.
2. Vital signs (blood pressure, weight [kg] and height [cm] SCREENING ONLY and ECOG performance status.
3. Smoking Questionnaire in Appendix A
4. CMP includes: serum chemistries (creatinine, glucose, total protein, blood urea nitrogen [BUN], total carbon dioxide [CO₂], albumin, total bilirubin, alkaline phosphatase, and aspartate transaminase [AST] and alanine transaminase [ALT]) and electrolytes (total calcium, chloride, potassium, sodium). CBC includes: platelets, ANC & HGB.
5. Repeat PT/INR and aPTT tests for subjects being screened for eligibility to cross over to pembrolizumab.

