7.3.3 Cross Over

Subjects receiving placebo will be eligible for cross over to treatment with pembrolizumab provided that eligibility outlined in section 3 is still met. (NOTE: Inclusion criteria #6 regarding initiation of study treatment within 2 to 6 weeks of completing first line chemotherapy only applies to initial randomization to placebo).

Cross over treatment should be initiated within 4 weeks of confirming eligibility. Subjects initiating treatment with pembrolizumab from placebo will follow the same schedule outlined in the study schedule of events in section 7 and receive up to 24 months of treatment unless progression or unacceptable toxicity is experienced.

Subjects initially randomized to placebo, who discontinue treatment due to unacceptable toxicity rather than progression, may be eligible for cross over to treatment with pembrolizumab provided resolution of the toxicity (or improvement to baseline), the eligibility outlined in section 3 is still met, and after discussion with the sponsor-investigator.

Subjects who cross over to pembrolizumab and discontinue treatment for any reason will follow the same study procedures as outlined above for the EOT visit.

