7.6 Determination of Progression/Post-progression imaging

Immunotherapeutic agents such as pembrolizumab may produce antitumor effects by potentiating endogenous cancer-specific immune responses. The response patterns seen with such an approach may extend beyond the typical time course of responses seen with cytotoxic agents, and can manifest as a clinical response after an initial increase in tumor burden or even the appearance of new lesions.

If radiologic imaging shows PD, tumor assessment should be repeated 4-6 weeks later in order to confirm PD with the option of continuing treatment per below while awaiting radiologic confirmation of progression. If repeat imaging shows a reduction in the tumor burden compared to the initial scan demonstrating PD, treatment may be continued as per treatment calendar. If repeat imaging confirms progressive disease, subjects will be discontinued from study therapy (exception noted Table 8) and the date of the original scan documenting progression will be considered the progression date. In determining whether or not the tumor burden has increased or decreased, site investigators should consider all target lesions as well as non-target lesions.

When feasible, subjects should not be discontinued until progression is confirmed; however, the decision to continue study treatment after the 1st evidence of disease progression is at the site investigator's discretion based on the clinical status of the subject as described in Table 7.

Subjects may receive study treatment while waiting for confirmation of PD if they are clinically stable as defined by the following criteria:

- Absence of signs and symptoms indicating disease progression
- No decline in ECOG performance status
- Absence of rapid progression of disease
- Absence of progressive tumor at critical anatomical sites (e.g., cord compression) requiring urgent alternative medical intervention

Table 7: Imaging and Treatment after Site-Assessed 1st Radiologic Evidence of PD

	Clinically Stable		Clinically Unstable	
	Imaging	Treatment	Imaging	Treatment
Site based assessment indicates PD	Repeat imaging 4-6 weeks later to confirm PD	May continue study treatment at the site investigator's discretion while awaiting confirmatory scan by site	Repeat imaging 4-6 weeks later to confirm PD per physician discretion only	Discontinue treatment

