8.5 Immune Related RECIST (irRECIST)

PFS, ORR and duration of response per irRECIST are defined as specified for the respective endpoints using RECIST 1.1 above, with the exception that a confirmation assessment of PD (4-6 weeks after the initial PD assessment) is required for subjects who remain on treatment following a documented PD per RECIST 1.1 (as detailed in section 7.6). The first date of progression, confirmed on the subsequent imaging study, will be considered the date of progression. Subjects who discontinue treatment following a documented PD assessment per RECIST 1.1 will be counted as having disease progression on the date of the documented PD assessment.

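### If the code is opened before progression is confirmed, the same unconfirmed first PD can count as a primary event on placebo and be set aside on pembrolizumab

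*Combined protocol and SAP*

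**What the plan says.** **Confirmation, both arms.** Section 7.6 states "If radiologic imaging shows PD, tumor assessment should be repeated 4-6 weeks later in order to confirm PD" and adds "When feasible, subjects should not be discontinued until progression is confirmed", leaving continuation to the investigator's discretion. Table 7, sections 7.3 and 7.5 and footnote 11 of the schedule ask for the same rescan in clinically stable subjects. None of them mentions the arm or whether the code is open.

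**Event definition.** Section 12.2 defines the primary endpoint as PFS by irRECIST. Under 8.5, "a confirmation assessment of PD (4-6 weeks after the initial PD assessment) is required for subjects who remain on treatment"; a subject who stops treatment after a documented PD is counted on the date of that PD. A confirmed PD is back-dated to the first scan.

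**Opening the code.** Section 7.3.2 lists "Time of treatment discontinuation due to disease progression" among its triggers and says the list is not exhaustive. To protect the primary endpoint it then gives two rules, both limited to subjects found to be on pembrolizumab. The second covers first progression: "Patients who are unblinded for a first progression event and confirmed to be on pembrolizumab, but who are considered clinically stable" may stay on treatment until the rescan, and beyond it if PD is not confirmed. Section 12.9 places unblinding at disease progression without saying confirmed.

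**Placebo after opening.** Section 6.1 offers cross-over at the time of progression. Footnote 1 of the schedule says "Subjects randomized to Arm A (placebo) who discontinue treatment due to progression or unacceptable toxicity will be eligible to cross over to pembrolizumab", and 7.3.3 gives the conditions. Under 12.6 only pre-cross-over placebo data enter the primary analysis.

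**The concern.** Section 8.5 makes the primary event depend on a treatment decision: stay on and confirmation is needed, stop and the first PD counts. While the blind holds, that decision cannot systematically follow the arm. Once the code is open it can. The opened pembrolizumab subject has a written route to continue and be rescanned. The opened placebo subject is on saline, has no matching rule in 7.3.2 and is offered active drug.

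Confirmed PDs do no harm, because back-dating gives the same event date in either arm. Bias can come only from first PDs that a rescan would not confirm. After early opening these can be dropped on pembrolizumab and kept on placebo, which adds early placebo events and pushes the one-sided 5% test towards pembrolizumab.

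**Working it through.** **1. Design inputs (12.5), reproduced first.** Control hazard: -ln(0.062)/12 = 2.781/12 = 0.232 per month, as stated. Full-effect hazard ratio, taking a linear fall from 1 at month 0 to θ at month 8: -ln(0.168)/0.2317 = 7.698 = 4(1+θ) + 4θ, so θ = 3.698/8 = 0.462, as stated. Sample size: N = (1.645 + 0.842)² V/μ² for the lag-weighted logrank, with censoring uniform over months 6-36 and a linear weight between months 2 and 3 (assumed, because Equation (5) of the cited method is not reproduced). A log-hazard-ratio drift gives N = 103 against the stated 104 (power 80.6% at 104); an exact-hazard drift gives 93. The point raised here does not change N.

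**2. One unconfirmed first PD, four paths.**

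| Path | Pembrolizumab | Placebo |
|---|---|---|
| Blind kept, treatment continues, PD not confirmed (7.6, 8.5) | no event | no event |
| Blind kept, treatment stopped at first PD (8.5) | event | event |
| Code opened at first PD, stays on treatment to the rescan | no event (7.3.2) | no event (8.5), but 7.3.2 has no rule for it |
| Code opened at first PD, stops or crosses over | event (8.5) | event (8.5); cross-over offered (6.1, 7.3.3) |

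Within each path the arms agree. The asymmetry is in which of the last two paths the text steers each arm towards. Nothing holds cross-over until the rescan: 7.3.3 asks for it within 4 weeks of confirming eligibility, while the rescan falls 4-6 weeks after first PD.

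**3. Placebo subjects affected.** Count = 52 × (share unconfirmed) × (share opened early) × (share of opened placebo subjects who stop before the rescan). With 10% unconfirmed and all of those opened stopping: 52 × 0.10 × 0.10 = 0.5 at 10% opened; 52 × 0.10 × 0.25 = 1.3 at a quarter; 2.6 at half; 5.2 if all. If 70% of first events are scan-detected, multiply by 0.7: 0.4, 0.9, 1.8 and 3.6. Censoring lowers these slightly.

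**4. Type I error by simulation.** No treatment effect; 52 per arm; hazard 0.232 in both arms; censoring and weight as in step 1; scans every 12 weeks (7.5). Assumed, because the documents give no figures: the share unconfirmed; the share opened early; 70-100% of first events scan-detected; the later PD either at the next scan or after a fresh exponential time rounded up to a scan. Worst case: every opened placebo subject stops before the rescan, and every unconfirmed PD on pembrolizumab is set aside.

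| Share opened early, 10% unconfirmed | One-sided type I error |
|---|---|
| 10% | 5.4-5.8% |
| a quarter | about 6-7% |
| half | about 6-10% |
| all (extreme) | about 7-16% |

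With no early opening the result is 4.8-5.7%, and with one rule in both arms 4.7-5.9%, so the excess comes from the asymmetry. At half opened, 5% unconfirmed gives 6.1-7.1% and 20% gives 7.6-14.7%. If only half of the opened placebo subjects stop before the rescan, half opened becomes 0.5 × 0.5 = 0.25, the quarter row: about 6-7%.

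The ranges reflect the models tried and are not bounds. With a fixed 12-week delay in continuous time, the error at 10% unconfirmed is only 5.5-5.6% even if all codes are opened.

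**The case against.** The best reply is that the protocol already has an arm-neutral rule. Sections 7.3, 7.5 and 7.6, Table 7 and footnote 11 ask for the rescan in any stable subject; 8.5 turns on treatment status, not arm; and the listed trigger in 7.3.2 is discontinuation for progression, which 7.6 would normally place after confirmation. An opened placebo subject who stayed on saline would still need confirmation. This stands, and it confines the problem to an exception path. It does not close that path: 7.3.2 itself provides for opening at a first PD, 12.9 does not say confirmed, and 7.3 sends the reader for confirmation details to 7.3.2, where they are written for pembrolizumab only.

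Second, section 7.6 attributes growth followed by response to immunotherapy, so unconfirmed PDs on saline may be few. If so, the excess shrinks towards nothing. This also stands; the documents give no rate for either arm.

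Third, PFS by RECIST 1.1, which needs no PD confirmation, is already a secondary endpoint (12.3). That is a real safeguard, but the plan does not tie it to this issue.

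Three stronger readings go too far:
- *Placebo progression never needs confirmation.* The text does not say this; the placebo consequence is inferred from the cross-over offer.
- *Opening for toxicity creates the same bias.* Section 7.3.2 does keep some pembrolizumab subjects on treatment ("Patients who are unblinded for toxicity and confirmed to be on pembrolizumab"), and 7.3.3 says "Subjects initially randomized to placebo, who discontinue treatment due to unacceptable toxicity rather than progression, may be eligible for cross over". But a placebo subject who crosses over without PD contributes only pre-cross-over data (12.6) and is therefore censored. The first-PD rule in 8.5 requires a documented PD.
- *The primary event must be redefined for every opened subject.* That would make the primary endpoint depend on an investigator's decision to unblind and would cost power, to repair a path of unknown frequency.

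**Conclusion.** The gap is real but narrow. On the path where the code is opened at a first PD before the rescan, the plan lets an unconfirmed PD be set aside on pembrolizumab and count on placebo. The direction favours pembrolizumab. The bias needs three things together: early opening, placebo stopped before the rescan, and a PD that the rescan would not have confirmed. The documents give no frequency for any of them, so the size cannot be derived. It is near nominal if early opening is rare, and becomes material only if early opening is common and most opened placebo subjects stop. I rate this a cheap improvement, with moderate confidence: the textual asymmetry is clear, its effect in practice is unknown.

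**What to change.** 1. In 8.5 and 12.6, pre-specify a sensitivity analysis of the primary irRECIST comparison with one event rule for both arms: *a subject whose code was opened at a first PD before the confirmatory scan is counted as progressed at that first PD, in either arm and whatever a later scan shows; all other subjects follow 8.5 as written.* Name the planned RECIST 1.1 PFS comparison as supporting it, and require the primary conclusion to be read against both.
2. Tabulate by arm: first PDs; codes opened before confirmation; subjects who stopped or crossed over before the rescan; PDs confirmed and not confirmed. This shows whether the path was used.
3. Reconcile 6.1, 7.3, 7.3.2, 7.6, 8.5 and 12.9 on when the code is opened relative to confirmation. No unblinding, continuation or cross-over rule is proposed here.

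**Cost.** One or two sentences in each of 8.5 and 12.6, one table, and cross-references. The primary endpoint and sample size stay as they are. In the sensitivity analysis a true pseudo-progression in an opened pembrolizumab subject counts as an event, so that analysis has somewhat less power. Under the design alternative with 12-week scans (simulated power 69-73%), the loss is 1-4 points if 5% of pembrolizumab subjects have one and half the codes are opened early, and 1-8 points if 10% do. With only 10% opened early it is under 1 and under 2 points. These rates too are assumptions.

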7.3.3 Cross Over

Subjects receiving placebo will be eligible for cross over to treatment with pembrolizumab provided that eligibility outlined in section 3 is still met. (NOTE: Inclusion criteria #6 regarding initiation of study treatment within 2 to 6 weeks of completing first line chemotherapy only applies to initial randomization to placebo).

Cross over treatment should be initiated within 4 weeks of confirming eligibility. Subjects initiating treatment with pembrolizumab from placebo will follow the same schedule outlined in the study schedule of events in section 7 and receive up to 24 months of treatment unless progression or unacceptable toxicity is experienced.

Subjects initially randomized to placebo, who discontinue treatment due to unacceptable toxicity rather than progression, may be eligible for cross over to treatment with pembrolizumab provided resolution of the toxicity (or improvement to baseline), the eligibility outlined in section 3 is still met, and after discussion with the sponsor-investigator.

Subjects who cross over to pembrolizumab and discontinue treatment for any reason will follow the same study procedures as outlined above for the EOT visit.

